2.7.3 Handling of missing values/censoring/discontinuations

Regarding ORR:

- Subjects in the FAS with unknown BOR will be noted as such in the appropriate tables/listings and counted as non-responders in the ORR calculation.
- If there is no baseline tumor assessment, all post-baseline overall lesion responses are expected to be 'Unknown'. If no valid post-baseline tumor assessments are available, the BOR must be "Unknown" unless progression or death is reported.
- If any new anti-neoplastic therapy is taken while on study, any subsequent assessments would be excluded from the BOR derivation.

- Confirmed PR or CR reported prior to any additional anticancer therapy will be considered as responses in the calculation of the ORR irrespective of the number of missed assessments before response.

Regarding DOR:

- If progression or death due to any reasons has not occurred by the date of the cut-off, then the subject will be censored following the same rules defined for PFS in [Section 2.5.3](#).
- If a subject with a CR or PR has no progression or death, the subject is censored at the date of last adequate tumor assessment.

Regarding OS:

- The last date the subject was known to be alive is the last date the subject was contacted or seen by the treating team. If no post-baseline dates are available (before death or a censoring reason occurred), the date of randomization will be used.
- If a subject is not known to have died by the date of the cut-off, OS will be censored at the last date the subject was known to be alive.

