Visit Name	Screening	Cycle 1	Cycle 2	Cycle 3	Cycle 4	Cycle 5	Cycle 6	Subsequent cycles (Up to 35 cycles)	EOT	Safety	Disease progression	Survival
Day	-28 to -1	1	1	1	1	1	1	1	-	30	-	Every 12 weeks
Capmatinib												
Antineoplastic therapies since discontinuation of study treatment										X		
Survival follow up												X

X = assessment to be recorded in the clinical database or received electronically from a vendor

S = assessment to be recorded in the source documentation only

1. Only applicable for subjects with local PD-L1 TPS data available for study eligibility. The PD-L1 TPS data tested locally should be recorded in eCRF

2. Within 72 hours prior to first dose of study treatment

6. Only the first eight subjects enrolled into the treatment arm with capmatinib need to take the intensive PK samples specified in [Table 8-7](#). Refer to [Table 8-8](#) for the rest of subjects.

7. If subjects experience an SAE or AE leading to the discontinuation of the study treatment, an unscheduled PK blood sample should be obtained whenever possible

8. Only when subjects who return to the site for safety follow up assessment

Final

Table 8-2b Assessment Schedule – applicable upon approval of protocol amendment 03

Visit Name	Treatment Phase - all cycles until end of study treatment or 35 cycles	EOT	30-Day Safety Follow-up
Adverse Events	X (continuous)		
Concomitant Medications	X (continuous, until 30 days after last dose of study treatment or start of new antineoplastic medication, whichever is sooner)		
Study drug administration pembrolizumab	X (day 1 of every cycle)		
X = assessment to be recorded in the clinical database			

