9.2.2 Follow up

9.2.2.1 Safety follow-up

All subjects receiving study treatment must have safety evaluations for 30 days after the last dose of study treatment. The 30 day safety follow-up can be done by telephone call or visit. Concomitant medications will be collected until the 30-day safety follow-up has been completed or the start of a new antineoplastic therapy, whichever occurs first. A PK and immunogenicity sample should be collected at the 30-day safety follow up visit as described in [Section 8.5.1](#). If the 30-day safety evaluation is conducted by phone, samples do not need to be collected.

Data collected should be added to the Adverse Events CRF, the antineoplastic therapies since discontinuation of study treatment CRF, the Concomitant Medications CRF and the PK/IG CRF. For female subjects of child bearing potential, pregnancy tests will be performed as outlined in [Section 8.4.3](#).

As of 04-Feb-2021, collection of PK and IG samples is terminated. Following approval of protocol amendment 03, antineoplastic therapies since discontinuation of study treatment will not be collected.

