9.2.2.3 Survival follow-up

Following approval of protocol amendment 03, survival follow-up will not be performed. Subjects will enter the survival follow-up period once they complete the safety follow-up and/or disease progression follow-up after treatment discontinuation (whichever is longer). Subjects will then be contacted by telephone every 12 weeks to follow up on their survival status. Any new antineoplastic therapies that have been started since the last contact date will also be collected during these phone calls.

Information on all subsequent therapies received for NSCLC, if any, after study treatment has been completed, will be collected (including start date, stop date, and date of progression if any).

10 Safety monitoring and reporting

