All adverse events must be treated appropriately. Treatment may include one or more of the following:

- Dose not changed
- Dose reduced/increased
- Drug interrupted/withdrawn

6. its outcome

If the event worsens, the event should be reported a second time in the eCRF noting the start date when the event worsens in toxicity. For grade 3 and 4 AEs only, if improvement to a lower grade is determined, a new entry for this event should be reported in the eCRF noting the start date when the event improved from having been Grade 3 or Grade 4.

Conditions that were already present at the time of informed consent should be recorded in medical history of the subject.

Adverse events (including lab abnormalities that constitute AEs) should be described using a diagnosis whenever possible, rather than individual underlying signs and symptoms.

Adverse event monitoring should be continued for at least 30 days following the last dose of study treatment.

Once an AE is detected, it must be followed until its resolution or until it is judged to be permanent (e.g. continuing at the end of the study), and assessments must be made at each visit (or more frequently, if necessary) of any changes in severity, the suspected relationship to the interventions required to treat it, and the outcome.

Progression of malignancy (including fatal outcomes), if documented by use of appropriate method (for example, as per RECIST 1.1 criteria for solid tumors), should not be reported as a serious adverse event. However, if the progression of malignancy is considered to be related to study treatment as per Investigator's assessment and meets the SAE definition, the event should be reported as a serious adverse event.

Adverse events separate from the progression of malignancy (i.e. deep vein thrombosis at the time of progression or hemoptysis concurrent with finding of disease progression) will be reported as per usual guidelines used for such events with proper attribution regarding relatedness to the drug.

Information about adverse drug reactions for the investigational drug can be found in the capmatinib Investigator's Brochure or the locally approved package insert of pembrolizumab.

Abnormal laboratory values or test results constitute adverse events only if they fulfill at least one of the following criteria:

- they induce clinical signs or symptoms
- they are considered clinically significant
- they require therapy

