10.1.3 SAE reporting

To ensure subject safety, every SAE, regardless of causality, occurring after the subject has provided informed consent and until 30 days following the last administration of study treatment must be reported to Novartis safety within 24 hours of learning of its occurrence. Detailed instructions regarding the submission process and requirements are to be found in the investigator folder provided to each site.

The following SAE reporting time frames apply:

1. Screen Failures (e.g. a subject who is screened but is not randomized): SAEs occurring after the subject has provided informed consent until the time the subject is deemed a Screen Failure must be reported to Novartis.
2. Randomized OR treated Subjects: SAEs collected from a subject signs ICF until 30 days after the subject has discontinued or stopped study treatment.

All follow-up information for the SAE including information on complications, progression of the initial SAE, and recurrent episodes must be reported as follow-up to the original episode within 24 hours of the investigator receiving the follow-up information. An SAE occurring at a different time interval or otherwise considered completely unrelated to a previously reported one must be reported separately as a new event.

If the SAE is not previously documented in the Investigator's Brochure or Package Insert (new occurrence) and is thought to be related to the study treatment, a Novartis Chief Medical Office and Patient Safety (CMO & PS) Department associate may urgently require further information from the investigator for health authority reporting. Novartis may need to issue an Investigator Notification (IN) to inform all investigators involved in any study with the same study treatment that this SAE has been reported.

Suspected Unexpected Serious Adverse Reactions (SUSARs) will be collected and reported to the competent authorities and relevant ethics committees in accordance with EU Guidance 2011/C 172/01 or as per national regulatory requirements in participating countries.

Any SAEs experienced after the 30 day period of safety follow up should only be reported to Novartis Safety if the investigator suspects a causal relationship to study treatment.

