2.1.1.5 On-treatment assessment/event and observation periods

For all safety reporting the overall observation period will be divided into three mutually exclusive segments:

- **pre-treatment period:** from day of subject's informed consent to the day before first administration of study treatment
- **on-treatment period:** from date of first administration of study treatment to 30 days after date of last administration of study treatment (including start and stop dates)
- **post-treatment period:** starting at Day 31 after last administration of study treatment.

If dates are incomplete in a way that clear assignment to pre-, on-, post-treatment period cannot be made, then the respective data will be assigned to the on-treatment period.

Safety summaries (tables, figures) include only data from the on-treatment period with the exception of baseline data which will also be summarized where appropriate (e.g., change from baseline summaries). In addition, a separate summary for death including on-treatment and post-treatment deaths will be provided. In particular, summary tables for AEs will summarize only on-treatment events, with a start date during the on-treatment period (treatment-emergent AEs).

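### Overall survival (OS) at 18 and 24 months, and the rest of the late OS curve, is kept although survival follow-up stops at approval of Amendment 03; unless approval came late, these estimates are likely too high

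*SAP*

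**What the plan says.** **Planned OS analysis.** SAP 2.7.2 asks for KM estimates on the FAS by arm: curve, median and quartiles, and values at 6, 12, 18 and 24 months with Greenwood intervals. SAP 2.7.3 sets the censoring rule: "OS will be censored at the last date the subject was known to be alive". SAP 2.1.1.6 takes that date from the last contact on or before a single data cut-off. SAP 2.1 runs the data until all subjects have finished treatment and safety follow-up.

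**What is still collected.** Protocol 9.2.2.3: "Following approval of protocol amendment 03, survival follow-up will not be performed". Table 8-2b, headed "applicable upon approval of protocol amendment 03", keeps only adverse events, concomitant medication and pembrolizumab dosing. Protocol 9.2.1 ends a subject's study at discontinuation plus safety follow-up, and 9.2.2.1 sets its length: "All subjects receiving study treatment must have safety evaluations for 30 days after the last dose of study treatment". Under Protocol 6.1.4.1, treatment no longer continues past progression. Under 6.1, subjects may leave for commercial drug.

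**How a later death could still arrive.** Protocol 10.1.1: "Adverse event monitoring should be continued for at least 30 days following the last dose of study treatment". Under Protocol 10.1.3, serious events after the 30-day period "should only be reported to Novartis Safety if the investigator suspects a causal relationship to study treatment". Protocol 10.1.1 also says that "Progression of malignancy (including fatal outcomes), if documented by use of appropriate method" is not a serious adverse event unless the investigator considers it treatment-related and it meets the definition. SAP 2.1.1.5 says "a separate summary for death including on-treatment and post-treatment deaths will be provided".

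**The concern.** The SAP keeps an OS analysis designed for 12-weekly survival calls after those calls have been withdrawn. Once a site approves the amendment, a subject who stops treatment is observed for about 30 days more and is then censored. Stopping is often due to progression, so censoring is tied to prognosis, whereas KM assumes that it is not.

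The sponsor recognised the effect of stopped data collection on PFS: SAP 2.5.2 drops the Bayesian model for that reason, and the censoring for PFS and best overall response was adapted. OS had no matching change. It has no minimum number at risk and no sensitivity analysis, and SAP section 4 reports no change from the protocol. A study report could therefore present 18- and 24-month OS, or a median, as FAS survival for a named secondary endpoint when the late part of the curve omits most deaths after progression.

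**Working it through.** **Treatment cap.** 35 cycles x 21 days = 735 days; 735 / 30.4375 = 24.1 months, which reproduces the protocol's figure of about 24 months.

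**Calendar limits.** Inputs: nobody treated by 22-Jan-2020 (Amendment 2, Study update); enrolment halted 21-Jan-2021 with 76 randomized (51 and 25); Amendment 03 dated 21-Apr-2021; month = 30.4375 days (SAP 2.1.1.3).
- 22-Jan-2020 to 21-Apr-2021 = 455 days = 14.9 months, the longest possible OS follow-up at the amendment date. A subject randomized on 21-Jan-2021 has 90 days = 3.0 months.
- 18 months: 22-Jan-2020 + 548 days = 23-Jul-2021.
- 24 months: 22-Jan-2020 + 730 days = 21-Jan-2022.
- Day 1 of cycle 34 is day 694, and 694 + 30 = 724, short of 730.5. Cycle 35 is day 715, and 715 + 30 = 745 (24.5 months). On an undelayed schedule only a subject reaching cycle 35 is at risk at 24 months through the safety window.
- 50 of 76 were ongoing on 15-Mar-2021, so 26 were not. Their 30-day windows ended by 14-Apr-2021, before the amendment date. Apart from minor routes they add no survival time after approval.

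**Size (illustrative).** The simulation censors at the later of approval and last dose + 30 days, with 400,000 subjects per scenario. From the documents: median OS 20.0 months (Protocol 1.1, pembrolizumab, PD-L1 of at least 50%) and median time to stopping 10.3 months (upper PFS value in Protocol 12.8). Assumed: exponential times, uniform entry from 22-Jan-2020 to 21-Jan-2021, and 25% of stops being deaths. Median survival after stopping is then 9.0 months. The implied monthly death hazard is 0.25 x ln2/10.3 = 0.017 on treatment and ln2/9.0 = 0.077 after it.

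| Approval, months after 21-Apr-2021 | 18 months: reported / complete follow-up | Difference, points | 24 months: reported / complete follow-up | Difference, points |
|---|---|---|---|---|
| 0 | 0.645 / 0.547 | +9.8 | 0.573 / 0.415 | +15.8 |
| 3 | 0.610 / 0.547 | +6.3 | 0.542 / 0.414 | +12.8 |
| 6 | 0.578 / 0.546 | +3.2 | 0.508 / 0.414 | +9.4 |
| 9 | 0.561 / 0.547 | +1.4 | 0.472 / 0.415 | +5.7 |
| 12 | 0.549 / 0.545 | +0.4 | 0.441 / 0.414 | +2.7 |

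With approval spread over 0 to 2 months the bias is about +9 and +16 points; over 9 to 11 months, about +1 and +4 to +5.

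Across median stopping times of 7.1 to 12.2 months and 10% or 25% of stops being deaths, approval at the amendment date gives 0.59 to 0.71 at 18 months and 0.51 to 0.67 at 24. Complete follow-up gives 0.54 to 0.55 and 0.41 to 0.42.

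**Median.** For approval at 0, 3 and 6 months the reported curve in the table is still above 0.5 at 24 months, although the model's median is 20.0. The median is therefore affected as well as the landmarks.

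**Risk sets.** In the table's scenario with approval at 0, about 23.8 of 76 are at risk at 18 months and 15.9 at 24. Split 51:25, that is about 16 and 8, then 11 and 5. All are on treatment or within 30 days of the last dose. If half move to commercial drug at approval, about 12 and 8 remain over both arms.

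**Mechanism check.** With equal death hazard on and off treatment, the simulated error at every landmark is within 0.6 points, which is simulation noise.

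**The case against.** **KM is a product from randomization.** A reader might infer that the 18- and 24-month values are survival of subjects who stayed on treatment. The documents do not support that: the estimates are on the FAS, and the early factors use all 76 subjects, including off-treatment deaths recorded before approval. Only the late risk sets are selected. This stands, and relabelling the values that way would be wrong.

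**Approval timing is unknown.** Amendment 3 requires ethics approval before implementation, so dates may differ by site. A reader might infer a large bias regardless; the table shows that at 18 months it nearly vanishes if approval took 9 months or more. This stands and makes the point conditional. The 24-month bias lasts longer.

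**Late deaths are not wholly lost.** Related serious events are still reported, and a summary of post-treatment deaths is planned. But documented fatal progression, the main expected cause, is normally outside serious-event reporting, so this helps only a little.

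**OS is descriptive and imprecise.** SAP 2.7.2 states no hypothesis. At 50% survival with complete follow-up, the 95% half-width is 1.96 x sqrt(0.25/25) = 20 points in the small arm and 1.96 x sqrt(0.25/51) = 14 in the large one. This limits the consequence, but a wide interval does not disclose a one-sided error.

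**Numbers at risk may already be planned** in the output shells, which are not available here. That would not change the estimates.

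**Conclusion.** The point holds in conditional form. The dates alone show that, where approval preceded about 23-Jul-2021 (18 months) or 21-Jan-2022 (24 months), the risk sets at those times consist essentially of subjects on treatment or within about 30 days of the last dose. The upward direction needs one assumption, that the death hazard is higher after stopping than on treatment. That is plausible because treatment stops at progression, but the documents do not show it. The size rests on approval dates that are not given and on assumed entry, stopping and survival patterns, so the figures are illustrative.

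The bias affects the median, quartiles and curve tail as well as the two landmarks. It does not invalidate the early curve: in the table's scenario with approval at 0, the reported values are 0.867 against 0.865 at 6 months and 0.733 against 0.701 at 12. No test or error rate is involved. It should be fixed before reporting, with medium confidence in its size.

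**What to change.** In SAP 2.7.2 and 2.7.3, and in 2.1.1.6 where a single cut-off is assumed:
- Add an OS analysis beside the planned one. Cut each subject's data at the date survival follow-up stopped at that subject's site, meaning site approval of Amendment 03. Count deaths on or before that date, and censor the others at the last date known alive on or before it. One common date at the earliest approval would discard valid follow-up elsewhere.
- Report OS landmarks, median and quartiles as FAS estimates only where this cut leaves a pre-specified minimum number at risk per arm; otherwise mark them not estimable. Do not then present the 18- and 24-month values of the planned analysis as FAS survival. The ten-responder condition in SAP 2.7.2 counts responders for duration of response and does not supply this minimum.
- Show numbers at risk per arm, and state that the planned curve is subject to informative censoring after follow-up stopped.

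**Cost.** SAP wording, recorded approval dates and one extra run. Fewer landmarks will be reportable, and some late deaths will appear only in the planned analysis and listings.

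Even 12 months may fail. With one common cut date and uniform entry, 11 to 16 of 76 are at risk at 12 months if approval was on 21-Apr-2021, 23 to 32 at +3 months and 34 to 48 at +6. If entry is assumed skewed late so as to match the 50 still ongoing, the counts are fewer than 1, 1 to 4 and 8 to 21.

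Under uniform entry the cut's 12-month error is within 0.3 points, or +0.2 to +2.8 if deaths are learnt only at the 12-weekly calls. Under late entry with that delay it reaches +0.8 to +13.8, where few or none are at risk, hence the minimum.

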2.8 Safety analyses

The Safety set will be used for summaries and listings of safety data.

2.8.1 Adverse events (AEs)

AE summaries will include all AEs occurring during on-treatment period. All AEs collected in the AE eCRF page will be listed along with the information collected on those AEs, (e.g., AE relationship to study drug, AE outcome, etc.). AEs starting during the post-treatment period will be flagged in the listings.

AEs will be summarized by number and percentage of subjects having at least one AE in each primary SOC and for each PT using MedDRA coding. A subject with multiple occurrences of an AE will be counted only once in the respective AE category. A subject with multiple CTCAE grades for the same PT will be summarized under the maximum CTCAE grade recorded for the event. AE with missing CTCAE grade will be included in the 'All grades' column of the summary tables.

In AE summaries by primary SOC and PT, the primary SOC will be presented alphabetically and the PT will be sorted within primary SOC in descending frequency. Tables by either primary SOC or PT will be sorted in descending frequency.

The following AE summaries will be produced for all subjects:

- Overview of AEs summarized by relationship and deaths (number and % of subjects who died, with any AE, any SAE, fatal SAEs, AEs leading to dose reduction/interruptions, AE leading to treatment discontinuation, AEs requiring concomitant or additional treatment);
- AEs by SOC and PT, summarized by relationship (all AEs and AEs related to study treatment);
- SAEs summarized by relationship (all SAEs and SAEs related to study treatment) and severity;
- AEs leading to treatment discontinuation (all AEs and AEs related to study treatment);

- AEs leading to study treatment dose reduction/interruption (all AEs and AEs related to study treatment);
- AEs requiring concomitant or additional treatment (all AEs and AEs related to study treatment);
- SAEs leading to fatal outcome (all SAEs and SAEs related to study treatment).

The following listings will be produced:

- All AEs (Safety set)
- AEs among subjects who were not treated (screening failure subjects)

The following summaries will be produced for all AEs observed (starting or worsening) during the on-treatment and/or post-treatment periods:

- AEs related to study treatment by SOC and PT;
- SAEs related to study treatment by SOC and PT

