Stage in cancer	The extent of a cancer in the body. Staging is usually based on the size of the tumor, whether lymph nodes contain cancer, and whether the cancer has spread from the original site to other parts of the body
Start of the clinical trial	The start of the clinical trial is defined as the signature of the informed consent by the first subject
Study treatment	Any single drug or combination of drugs or intervention administered to the subject as part of the required study procedures
Study treatment discontinuation	When the subject permanently stops taking any of the study drug(s) prior to the defined study treatment completion date (if any) for any reason; may or may not also be the point/time of study discontinuation
Subject	A trial participant (can be a healthy volunteer or a patient)
Subject number	A unique number assigned to each subject upon signing the informed consent. This number is the definitive, unique identifier for the subject and should be used to identify the subject throughout the study for all data collected, sample labels, etc.
Treatment arm	A treatment arm defines the dose and regimen or the combination, and may consist of 1 or more cohorts.
Variable	A measured value or assessed response that is determined from specific assessments and used in data analysis to evaluate the drug being tested in the study
Withdrawal of study consent (WoC)	Withdrawal of consent from the study occurs only when a subject does not want to participate in the study any longer and does not allow any further collection of personal data

Amendment 3 (21-Apr-2021)

Amendment rationale

The main purpose of this amendment is to modify the study conduct and data analysis following the enrollment halt on 21-Jan-2021 due to lack of tolerability observed in the capmatinib plus pembrolizumab arm. The decision to halt enrollment, supported by the Data Monitoring Committee (DMC), was made based on the observation that subjects who receive capmatinib plus pembrolizumab combination treatment had higher rates of SAEs/AEs, leading to dose interruption and/or discontinuation of both study treatments compared to subjects in the pembrolizumab single agent arm.

Immediately following the enrollment halt, below procedural changes have been performed:

- Capmatinib treatment was discontinued in subjects on the combination arm. All ongoing subjects continue to receive single-agent pembrolizumab, a registered and commercialized treatment for the study indication.

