12.5.2 Safety endpoints

For all safety analyses, the safety set will be used. All listings and tables will be presented by treatment arm.

The overall observation period will be divided into three mutually exclusive segments:

Pre-treatment period:

- from day of subject's first informed consent to the day before first administration of study treatment

On-treatment period:

- Single agent arm: from date of first administration of study treatment to 30 days after date of last actual administration of any study treatment (including start and stop date).
- Combination arm: from date of first administration of any study drug to 30 days after date of last actual administration of any study drug (including start and stop date).

Post-treatment period:

- Single agent arm: starting at day 31 after last administration of study treatment.
- Combination arm: starting at day 31 after the last administration of study treatment.

Safety summaries (tables, figures) include only data from the on-treatment period with the exception of baseline data which will also be summarized where appropriate (e.g. change from baseline summaries). In addition, a separate summary for death including on treatment and post treatment deaths will be provided. In particular, summary tables for adverse events (AEs) will summarize only on-treatment events, with a start date during the on-treatment period (treatment-emergent AEs).

The on-treatment period lasts from the date of first administration of study treatment to 30 days after the date of the last actual administration of any study treatment.

Adverse events

All information obtained on adverse events will be displayed by treatment arm and subject. Summary tables for adverse events (AEs) will include only AEs that started or worsened during the on-treatment period, the **treatment-emergent** AEs. The incidence of treatment-emergent adverse events (new or worsening from baseline) will be summarized by system organ class and or preferred term, severity (based on CTCAE grades), type of adverse event, relation to study treatment. Serious adverse events and non-serious adverse events during the on-treatment period will be tabulated. All deaths (on-treatment and post-treatment) will be summarized.

All AEs, deaths, and serious adverse events (including those from the pre and post-treatment periods) will be listed and those collected during the pre-treatment and post-treatment period will be flagged.

Vital signs

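### Adverse events are tabulated by arm only as crude percentages over on-treatment windows whose length may differ by arm, with no summary that accounts for time at risk

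*SAP*

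**What the plan says.** The measure is a proportion of subjects. SAP 2.8.1 says that "AEs will be summarized by number and percentage of subjects having at least one AE in each primary SOC", and adds: "A subject with multiple occurrences of an AE will be counted only once in the respective AE category". SAP 2.8.4 uses the number and percentage of subjects with at least one event for each adverse event of special interest (AESI).

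The window is the on-treatment period: "AE summaries will include all AEs occurring during on-treatment period". SAP 2.1.1.5 runs it "from date of first administration of study treatment to 30 days after date of last administration of study treatment". For the combination arm, SAP 2.1.1.2 takes the last dose of either component as the last administration. Protocol 12.5.2 agrees: "Combination arm: from date of first administration of any study drug to 30 days after date of last actual administration of any study drug".

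Exposure is summarized by arm in SAP 2.4.1 but is never the denominator of an adverse event summary. Neither document plans an event rate per person-time, a time-to-first-event analysis, or a table over a common fixed window. Three outputs depart from the main pattern: treatment-related AEs and SAEs over the on- and/or post-treatment periods (SAP 2.8.1), the registry tables that count repeat occurrences (SAP 2.8.3), and the death summaries and listings. None of these is adjusted for time at risk.

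The Amendment 3 rationale in the protocol gives the reason for the enrolment halt: combination subjects had "higher rates of SAEs/AEs, leading to dose interruption and/or discontinuation of both study treatments compared to subjects in the pembrolizumab single agent arm".

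**The concern.** The window rule is the same in both arms, but the realized window is set by how long each subject stays on treatment, up to 35 cycles. If subjects in one arm stop all treatment sooner, they are observed for less time, and fewer of them will show an event that accrues over time, even at the same underlying rate. The Amendment 3 statement makes different treatment durations a documented possibility here.

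Characterizing safety by arm is a secondary objective, and tolerability is why the trial was halted. With efficacy reduced to Kaplan-Meier description, the safety tables become a main output. They show the arms side by side, so readers will compare them whether or not a test is planned.

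**Working it through.** **Inputs.** Neither document states a window length or an AE rate for this trial, so there is no planned figure to reproduce. The rates and durations below are assumptions shown as a range. Documented inputs are the 30-day extension (SAP 2.1.1.5) and the month length of 30.4375 days (SAP 2.1.1.3).

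**Step 1: fixed windows, constant and equal rate.** The chance of at least one event in a window of W months at rate h per month is 1 − exp(−h × W). For example, at h = 0.10, W = 4 gives 1 − exp(−0.4) = 33% and W = 8 gives 1 − exp(−0.8) = 55%.

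| Rate per month | 4 vs 8 months | Gap (points) | 6 vs 9 months | Gap (points) |
|---|---|---|---|---|
| 0.05 | 18% vs 33% | 15 | 26% vs 36% | 10 |
| 0.10 | 33% vs 55% | 22 | 45% vs 59% | 14 |
| 0.15 | 45% vs 70% | 25 | 59% vs 74% | 15 |

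The rates are equal by construction, so the whole gap comes from the windows.

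**Step 2: treatment time varies between subjects.** With exponential treatment time of mean m months plus 30 days (30/30.4375 = 0.986 months), the chance is 1 − exp(−0.986h)/(1 + hm). At h = 0.10:
- m = 8: 1 − 0.906/1.8 = 49.7%.
- m = 4: 1 − 0.906/1.4 = 35.3%.
- m = 6: 43.4%, so a milder imbalance of 8 versus 6 months gives a gap of about 6 points.

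**Step 3: early-onset events.** Put all the risk in the first 6 weeks, with 30% cumulative incidence, and keep the exponential treatment times plus 30 days. Crude incidence is then 29.8% vs 29.6% for means of 8 vs 4 months, and 29.8% vs 29.3% for 8 vs 2 months. The artefact almost disappears.

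**Step 4: does a person-time rate remove it?** The setting of step 2 with h = 0.10 was simulated with 1,000,000 subjects per arm. First events were divided by time to first event or end of window. Crude percentages were 49.6% and 35.2%. The rate was 0.100 per month in both arms, or 10.0 per 100 subject-months.

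**Step 5: which way do the windows differ in this trial?** Setting the provisions side by side:
- Amendment 3 says interruption and/or discontinuation. Interruption alone does not move the date of the last dose.
- Protocol 6.7.2 lets the other drug continue when one is stopped for an unresolved AE, and the window closes only after the last dose of either drug.
- When the sponsor stopped capmatinib, ongoing combination subjects continued on pembrolizumab and stayed inside the combination arm's window. On 15-Mar-2021, 50 of the 76 randomized subjects (51 combination, 25 pembrolizumab alone) were still on treatment. The split by arm is not given.
- In both arms treatment can also end at progression or, under Protocol 6.1 and 9.1.1, on transfer to commercial pembrolizumab.

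These provisions pull in different directions, so the documents do not show which arm had the shorter windows.

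**Step 6: a pooled combination rate has its own problem.** Suppose the rate is 0.15 per month on capmatinib and 0.05 after it stops, with equal person-time in each segment. The pooled rate is (0.15 + 0.05)/2 = 0.10, which hides the excess on capmatinib. Person-time therefore has to be separated at the stop of capmatinib.

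**The case against.** The strongest reply is that percentages are what the objective asks for. The endpoint is incidence and severity of AEs, the aim is to characterize each arm, and no between-arm test is planned. Exposure is tabulated by arm, so a reader can see an imbalance, and every AE is listed. An AE that itself causes treatment to stop is always counted, so the signal that led to the halt is the least hidden. This stands, and it means that no stated objective fails. It does not help a reader who sees unequal exposure and unequal percentages and has no means of combining them.

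The second reply is that the size depends on favourable assumptions: constant hazard, equal hazards, and one window half or two thirds as long as the other. No passage supports those ratios, and Amendment 3 reports higher AE rates in the combination arm, not equal ones. This also stands. The gaps above illustrate the mechanism and do not estimate this trial.

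A reader might infer that the planned tables make the combination arm look safer than it is. The documents do not support that reading. They do not say that combination subjects had shorter windows, and pembrolizumab-only time after capmatinib stopped still counts for that arm.

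**Conclusion.** The plan has no adverse event summary that accounts for time at risk, and it was written when differential stopping had already been reported. If realized windows differ by arm, crude percentages mix rate with observation time for events that accrue over time. The effect ranges from near zero for early-onset events to about 10 to 25 points under a constant, equal hazard of 0.05 to 0.15 per month with assumed windows of 6 vs 9 or 4 vs 8 months. The net direction in this trial cannot be fixed from the documents. This is a worthwhile, inexpensive addition to the safety reporting. It does not show that the existing tables are biased toward either arm.

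**What to change.** Keep the percentages. In SAP 2.8.1 and 2.8.4 add, by arm, the exposure-adjusted incidence rate: subjects with a first event per 100 subject-months at risk, with time stopped at the first event or the end of the on-treatment window, and a 95% confidence interval. Do this for any AE, grade 3 or higher AE, SAE, AEs leading to interruption, reduction or discontinuation, and each AESI. Dose reduction is defined only for capmatinib (SAP 2.4.2), so that row describes the combination arm alone.

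In the combination arm, also present events and person-time separately before and after the stop of capmatinib. Define the cut date for each subject, covering both individual stops and the sponsor's decision.

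The cost is modest but not nil. Dosing dates and AE start dates are collected, and SAP 5.1.2 already imputes partial start dates. However, the exposure variables in SAP 2.4.1.1 and 2.4.1.2 are not time at risk: they lack the 30-day extension and the truncation at first event, which must be derived for each category. The rates also assume a roughly constant hazard and can mislead when events cluster early, so they supplement the percentages and do not replace them. Widening the window would not do the same job, because routine AE collection ends 30 days after the last dose.
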